### **Range of Testable Acuity**

If the child is unable to see the largest (20/800) stimulus at the 3M testing distance, the testing will be conducted at 1 meter. The same procedure will be followed at 1 meter as was used at 3 meters. If the child is unable to detect the 20/800 stimulus at 1 meter (ie, VA < 20/2400), then the E-ETDRS testing will be stopped for this eye and the test for Hand Motion will be performed.

### **Assessment of Hand Motion Vision**

The examiner's hand is extended to about two feet in front of the eye being tested; the fellow eye is occluded. With a light shining from behind the patient onto the examiner's hand, the hand is moved either up-and-down or side-to-side in front of the eye at a steady speed of about one cycle/second. The patient is asked to identify the direction of motion of five separate trials. Four out of five correct responses indicate the presence of Hand Motion vision. If fewer than four responses are correct, check for Light Perception vision.

### **Assessment of Light Perception**

Children who are unable to perform E-ETDRS or Hand Motion testing in the treated eye will have that eye assessed for the presence of light perception (LP). LP will be tested with an indirect ophthalmoscope. Testing for LP will take place in a darkened room. Because the LP testing needs to be done monocularly, it is necessary to block the eye not being tested from all possible light to preserve accuracy. Standard eye patches alone do not achieve complete occlusion, and for this reason the tester, parent, or helper will place the palm of his or her hand gently but firmly over the patched eye thereby blocking out all light. The bright light from the indirect ophthalmoscope will then be directed at the uncovered eye 3 or 4 times from the front and sides at 18 – 24 inches from the face to avoid exposing the child to the heat of the light. The tester will ask the child to respond when the light is seen or to watch for consistent changes in

behavior occurring only when the light is being presented, such as eye movement towards or away from the light or head turn towards or away. If the examiner is convinced that the child does not perceive light, the vision will be recorded as No Light Perception.

### **Pachymetry**

Pachymetry will be performed using the Pachmate (DHG Technology) or similar pachymeter after the instillation of a topical anesthetic drop. The probe tip will be touched to the center of the cornea and measurements will be taken until there is 1 with a SD <10 microns.

### **Optical Biometry**

#### **Axial Length**

Biometry to determine axial length will be performed on both eyes using the non-contact instrument, the IOLMaster (Carl Zeiss Meditec, Dublin, CA) or Lenstar (Haag-Streit USA, Mason, OH). At least three measurements will be obtained for each eye and then averaged to hundredths of a millimeter. Both the raw data/scan and the summary page is to be printed out and faxed to the DCC.

#### **Keratometry**

Keratometry readings will be obtained using the IOLMaster or Lenstar. The AUTO mode will give the average of three measurements; two such averages should be obtained for each eye and their average recorded. Manual keratometry may be done if necessary.

#### **Corneal Diameter**

Corneal diameter will be taken from the IOLMaster or Lenstar biometry print-out.

### **Indirect Ophthalmoscopy**

Indirect ophthalmoscopy will be performed on the dilated eyes to determine the cup-to-disc ratio and to assess the health of the optic nerve and retina.

## **QUALITY OF LIFE MEASURES**

Caretakers will be given a packet of questionnaires to take home. These are to be completed by either the primary caretaker or the study participant. They will be accompanied by detailed instructions and a stamped, addressed envelope for returning them to the Coordinating Center.

The questionnaires are:

Pediatric Quality of Life Inventory (PedsQL)

Effects of Youngsters' Eyesight on Quality of Life (EYE-Q)

Child Behavior Checklist

Self-Perception Profile for Children

Participation and Environment Measure for Children and Youth (PEM-CY)

Parenting Stress Index, Short Form (PSI-SF)

## **CHAPTER 4 IMAGING**

### **Anterior Chamber OCT (AC OCT)**

Anterior Chamber OCT will be performed on the undilated eyes. We prefer to use the Heidelberg SPECTRALIS spectral domain OCT machine. Heidelberg has created an anterior segment analysis lens and a specialized program. The Heidelberg SPECTRALIS anterior segment module, ASM, was approved by the FDA in March 2012 (Heidelberg Corporation, 2012). Leung et al. (Leung CK, 2008) found high reproducibility of results with the Heidelberg OCT along with agreement with gonioscopy findings. It is performed prior to instillation of any dilating drops.

### **Optic Disc Photos**

Stereoscopic disc photographs are an established means of evaluating optic discs for glaucomatous damage. All patients will have stereoscopic disc photographs taken after dilating the pupils. Dilation will be performed prior to obtaining optic disc photographs. Simultaneous stereo images centered on the optic disc should be performed on both eyes using a digital fundus camera. The resolution of the disc photos should be such that the disc margins and vasculature are clearly visible. Disc photographs will be reviewed independently by three ophthalmologists with expertise in pediatric glaucoma ([name], [name], and [name]). Photographs will be graded as normal, glaucoma suspect, or glaucomatous optic neuropathy primarily by comparing the appearance of the study eye to the fellow eye. Disc photographs were not part of the Phase 1 or 2 protocols due to the difficulty of obtaining high quality photographs in very young children.

### **Optic Nerve Fiber Layer OCT**

Spectral domain optical coherence tomography (SD-OCT) has been shown to be a powerful tool evaluating and managing adults with glaucoma, and can even predict among glaucoma suspect those eyes at higher risk for developing visual field loss (Mwanza et al., 2011; Miki et al, 2014). In children, peripapillary retinal nerve fiber layer thickness (RNFL) assessed by either time domain OCT [Hess et al; Nadeau et al., 2010] or, more recently, by SD-OCT [Alasil et al, 2013], has been shown to be effective in differentiating between normal eyes and eyes with glaucoma (Ghasia et al., 2013; Srinivasan et al, 2014). RNFL measurements of both eyes will be taken using the Heidelberg Spectralis OCT by a trained OCT imager, with a baseline signal strength of at least 25. Average RNFL will be compared between the surgical and the normal fellow eyes for all subjects, the latter serving as the control group. Average RNFL will be compared among study eyes with glaucoma suspect or glaucoma status, and those without a glaucoma-related adverse event. Quadrant level analysis of RNFL thickness will be carried out to detect trend in thinning among those with glaucoma-related adverse events compared to normal fellow and unaffected study eyes. Similarly, the difference in average RNFL between study and control fellow eyes will be compared for children with glaucoma suspect, glaucoma, and those with neither. Average RNFL will be correlated with optic nerve head cupping and the presence or absence of glaucomatous optic neuropathy (assessed by masked review of stereophotographs) across all study eyes.

The OCT data will be submitted digitally so that they can be reviewed remotely without copy/fax/scan issues. Evaluation will consist of a look at the mean NFL, the superior/inferior/nasal/temporal quadrant numbers, and symmetry with the fellow eye.

## **CHAPTER 5 STATISTICAL CONSIDERATIONS & DATA CAPTURE AND MANAGEMENT**

### **Study Design**

IATS is a randomized controlled clinical trial with patients originally assigned to either CL or IOL as a correction for aphakia after cataract surgery. During Phases 1 and 2, investigators diligently avoided implanting a secondary IOL in patients randomized to CL correction except when it would be in the best interest of the child to have a secondary IOL because of lack of compliance with CL correction. Steering Committee approval was required before a secondary IOL could be implanted and documentation of the efforts to improve CL compliance had to be submitted before approval was granted. No child randomized to CL received a secondary IOL before the vision test at 12 months of age. As of December 2013 when all 57 study participants who were randomized to CL completed the study, only 3 had received a secondary IOL before the 5Y visit. Since the 5Y visit, 16 children in the CL group have received secondary IOLs.

### **Glaucoma**

At age 1 year we did not find a statistically significant difference in the percent of patients with glaucoma/glaucoma suspect between the IOL and CL treatment groups (16% vs 9%, respectively,  $p = 0.39$ , 95% CI for difference = 6% - 21%). At 5 Years, those numbers were higher (CL 35% and IOL 28%), but were still statistically equal. We hypothesize that newly diagnosed glaucoma/glaucoma suspect will occur more frequently between the ages of 5 and 10 years in the study eyes randomized to the CL group resulting in a higher cumulative incidence of glaucoma in this group. The percent of patients with glaucoma at 10 years of age will be compared between the treatment groups using Fisher's exact test. As described above under the statistical considerations for visual acuity, we expect very little missing data. We will conduct sensitivity analyses comparing results for patients examined at 10 years of age with results in which patients not examined at 10 years who did not previously have glaucoma will be assumed to either have or not have glaucoma at 10 years of age. Patients not examined at 10 year of age who were previously diagnosed with glaucoma will retain that diagnosis in the sensitivity analyses, since per the IATS protocol, once a patient is diagnosed with glaucoma the patient is considered to have glaucoma for the remainder of the study.

We expect that the percentage of patients with glaucoma in treated eyes will double between the age 1 and 10 year examinations in the CL group whereas the percent will remain largely unchanged in the IOL group.

### **Data Capture and Management**

Data management procedures for this new phase of IATS have been designed with the following in mind: (1) Newly captured data will need to be integrated with the extensive IATS database from phases 1 and 2 in order to accommodate the scientific work needed to address the specific aims of the study, especially those involving longitudinal analyses; (2) many of the clinical center and Data Coordinating Center (DCC) staff from earlier phases of IATS will be working on the new phase; (3) FDA regulatory and reporting requirements will continue to apply to IATS, as they have in the past; (4) the development, refinement, implementation and maintenance of data management procedures must be efficient and streamlined, especially since the new phase involves just one clinical examination of each subject.

The DCC staff, data management programming and procedures for the new phase of IATS have been streamlined, and leverage the experience, existing infrastructure and resources of the current IATS DCC. Leveraging existing resources, rather than developing, implementing, refining and maintaining brand new systems for data management for the new phase that are separate from the systems for previous phases of IATS, is the most efficient approach, and is likely to have a direct and positive impact on data quality and scientific work in the study.

Data will be captured and managed using the latest, internet-based electronic data capture (EDC) modules that are part of Clinical DataFax Systems Incorporated's (CDSI) client-server data management software, iDataFax and DataFax (hereafter referred to as iDataFax). The data management system used in previous phases of IATS was based on earlier versions of the same CDSI software system, and is currently maintained by DCC staff using the latest version of this system. The DCC team that is in place is smaller than in past phases, but has extensive experience with CDSI's software, as is detailed in the sections below. Clinical center staff from the previous phases of IATS also have experience interacting with CDSI's data management system, especially in terms of receiving and responding to quality control reports generated by the system. The main difference for clinical staff in the new phase is that their data will be electronically entered into and captured by the system, instead of case report forms having to be faxed into it. The small amount of training that is required to become proficient in the use of CDSI's EDC module will be provided the DCC staff who have extensive experience in doing so. Strict and extensive quality control programming and procedures are in place in the existing data management system for IATS. The continued use of CDSI's software, iDataFax, will allow for the programming and procedures to be efficiently extended into the new phase, will provide the best chance for maintaining the highest data quality, and will make it possible for us to continue to meet FDA regulatory and reporting requirements in the most efficient and rigorous manner.

### Data Capture, Flow and Handling

A diagram of the systems for data capture, management and statistical reporting and analysis is shown in the "IATS Data Flow" figure below. The coordinator at each clinical site will record exam data on paper source document worksheets, and will then enter them into an electronic Case Report Form (eCRF) using the iDataFax EDC module installed on a local computer. The eCRF will look exactly like the source document worksheet, since the latter forms the background of the image on the EDC module screen into which the data are entered. The current drafts of the eCRFs and the source document worksheets will duplicate the eCRFs in format. The EDC module is able to connect to the main database on a server at the DCC, and will automatically store the data there in real time. Edit checks for data field validity will be applied at data entry time, and additional edit checks will be applied using nightly batch jobs running on the main server at the DCC. Any data issues will be marked by a query that describes the problem. Queries will be emailed to the clinical centers as a Quality Control Report (QC Report) on a monthly basis. Clinical coordinators fix most problems by making changes to the eCRF via the EDC module, which changes the query status from outstanding to

[figure not shown]
pending central review. The DCC clinical data manager will review the eCRF edits on a weekly basis and the queries will be either reinstated for further clarification or marked as resolved. iDataFax maintains an audit trail of eCRF edits made by both clinical center and DCC personnel.

Medical records such as clinical records related to adverse events and operative reports will also be submitted to the system via the EDC module as scanned images, which can be attached to the relevant eCRF page in the database.

For the purposes of remote monitoring of clinical sites, the clinical sites will upload scanned source document worksheets requested by the Clinical Data Manager at the DCC. The Clinical Data Manager will compare source document worksheets against electronically entered data. Discrepancies will result in queries being marked in the system, which will be included in the regular QC Report.

iDataFax can export data in forms that can be read by commonly used statistical analysis software packages. Daily exports from iDataFax will be performed by batch jobs running on the main server. Daily automated batch routines developed by the DCC Statistical Programmer will import the data into SAS data sets. These data sets will be used for standard analysis and reporting, performed on a weekly basis, for the purpose of providing information at regular executive and steering committee meetings. Department of Biostatistics and Bioinformatics personnel have developed a system of S-Plus functions that produce the code for making tables and graphs in LaTeX, a mark-up language commonly used in mathematical fields for document processing. This system has been in use in previous phases of IATS, and will continue to be maintained, refined and used in this new phase for the purposes of producing standard reports for the FDA.

## IATS Data Flow

### Data Storage and Security

The electronically captured study data will reside exclusively on a secure, firewall- and password-protected Unix server at the Rollins School of Public Health (RSPH) of Emory University. The server is described in detail in the Facilities and Other Resources section of this grant application. It is housed in the locked server room of the RSPH, to which only certain staff members of the RSPH information technology (IT) group have keys. RSPH IT staff maintain the server, and perform daily incremental, and weekly full backups.

The data management system on the server will be accessed by IATS DCC staff from within the RSPH building via the school's secure internal network. At clinical centers, access to the EDC system will be limited to authorized personnel at the clinical centers (the center coordinator and PI), who will have access only to the data for their centers. The EDC module of iDataFax is compliant with all regulatory requirements including e-signatures, audit trails, and rules for password complexity, aging and notification. All changes to the database, at the data record and individual data field level, are recorded and include the id of the user making the change and the date and time of the change. The transmission of entered data and pdf files over the internet uses 128 bit SSL encryption.

### Clinical Center Monitoring

Regular (weekly) Quality Control (QC) reports will be issued for each clinical center detailing eCRF data quality issues. DCC staff will continuously monitor eCRFs to ensure that

- all eCRFs are completed

- all eCRFs are up to date
- entered data are complete, accurate and follow study protocol and procedures.
- all eCRF corrections have been completed since last QC report

In addition to these weekly QC reports, we will implement a centralized, risk-based plan for remote monitoring of site study activities that is based on the specifications included in the “FDA Guidance for Industry: Oversight of Clinical Investigations – A Risk-Based Approach to Monitoring” (US Department of Health and Human Services, Food and Drug Administration, 2013). The DCC Associate Director and Clinical Data Manager, in collaboration with the Study Chairman, will identify critical data elements and study administration or regulatory processes to be monitored and reviewed. At the Clinical Data Manager’s request, the clinical sites will upload scanned source document worksheets and any other requested clinical or regulatory records using the EDC module of iDataFax. The Clinical Data Manager will compare source document worksheets against electronically entered data to review their accuracy, and will review and evaluate other uploaded documents as appropriate. Discrepancies will result in queries being marked in the system, which will be included in the regular QC Report. Remote monitoring of each clinical site will be performed on an ongoing basis.

### **Statistical Analysis**

Descriptive analyses will be conducted to characterize the study population and detect potential selection bias as a result of missing data, dropouts or noncompliance/non-adherence. Two-sample t-tests will be used to compare continuous variables between two treatment groups. For continuous variables that are not normally distributed, appropriate transformations will be applied before normality-based tests are used or nonparametric tests such as Wilcoxon tests will be used as appropriate. Chi-square tests or Fisher’s exact tests will be used to compare categorical variables between groups.

All primary analyses will be intention-to-treat. The percent of patients with glaucoma/glaucoma suspect at 10 years of age will be compared between the treatment groups using Fisher’s exact test. We will also explore the role of baseline characteristics in the development of the primary endpoint using logistic regression and the Akaike information criterion (AIC; Akaike, 1974) will be used for model selection. In addition to analyzing the percent of patients who develop glaucoma/glaucoma suspect at any time up to age 10, we will also investigate analyzing the time to the primary endpoint using survival analysis methods, including the product-limit method to estimate the probability of developing glaucoma/glaucoma suspect versus time after surgery, comparing the time to developing glaucoma/glaucoma suspect between treatment groups with a log-rank test, and exploring the role of baseline characteristics with proportional hazards regression. The use of survival analysis methods may be problematic depending on how successfully we are able to determine the date of diagnosis, particularly for those patients who develop glaucoma/glaucoma suspect between 5 and 10 years of age when patients are not being examined within the study. Of note, patients not examined at 10 years of age who were previously diagnosed with glaucoma/glaucoma suspect will retain that diagnosis in all analyses, since per the IATS protocol, once a patient is diagnosed with glaucoma/glaucoma suspect the patient is considered to have glaucoma/glaucoma suspect for the remainder of the study.

As secondary analyses, we will repeat the aforementioned analyses for the secondary endpoint of glaucoma. In addition, we will use logistic regression for a multinomial outcome (proportional odds models or baseline logic models) to analyze the three categories, Glaucoma, Glaucoma Suspect, and normal (not glaucoma/glaucoma suspect) jointly.

Linear mixed models (LMMs) will be used to characterize the change in refractive error over time for both the treated and fellow eyes in the IOL group and to compare the changes in the treated eyes of the two treatment groups. In addition, LMMs will be used to identify baseline risk factors such as age of cataract surgery and axial length and other factors that arise during childhood, such as amblyopia and glaucoma, that are associated with a larger than expected myopic shift in the IOL group.

We will use two approaches for handling missing data as needed. First, we will use the available-case approach (Little and Rubin, 2002), i.e., conducting the proposed analyses excluding patients for whom the glaucoma/glaucoma suspect status is not verified at 10 years. Second, we will use the approach of multiple imputation (Little and Rubin, 2002) before conducting the proposed analyses and we will also conduct sensitivity analysis (Little et al., 2012). In addition, to correct for potential selection bias as a result of non-adherence to patching in early years and/or having a secondary IOL in the CL group, we will use approaches including instrumental variable and propensity scores (Little et al., 2009; Rosenbaum and Rubin, 1983). In addition, in case there are deviations from the target date for the outcome measurement, we will adjust for the time of the outcome measurement in our analyses as appropriate.

In addition to development of glaucoma, other clinical outcomes will also be measured and the analysis methods to be used in describing those outcomes are as follows.

**Visual Acuity:** For visual acuity at 10 years of age, we intend to use the Wilcoxon rank-sum test to compare the median visual acuities of the two treatment groups, with the patients included in the treatment group to which they were randomly assigned (intention-to-treat). As described in the section above (Status of Patients between Phases 2 and 3), among the patients randomized to CL who have thus far completed the 5 year of age exam, 38% have had secondary IOL implantation (insertion of an IOL after the initial cataract surgery). Thus, unlike in Phase 1 (1 year of age) when none of the contact lens patients had a secondary IOL and in Phase 2 (5 years of age) when only 2 contact lens patients had received a secondary IOL, for Phase 3 (10 years of age), a substantial percent of the patients in contact lens group will have a secondary IOL. Therefore, for visual acuity at 10 years of age, IATS will be a comparison between one treatment in which patients have an IOL inserted at the time of the cataract surgery and a second treatment in which patients are initially treated with a contact lens with the option of implanting a secondary IOL after 5 years of age. Analyses that attempt to address the question of a secondary IOL versus no IOL would likely be fraught with bias. Although the decision to have a patient undergo secondary IOL implantation is largely one of physician and parental preference, the condition of the patient is also a factor. For example, a secondary IOL would not be implanted in a patient with extremely poor vision. Therefore, such comparisons will be avoided.

In addition to the analysis to compare visual acuity at age 10 between the treatment groups, we will also investigate the relationship between baseline factors and the visual acuity at age 10. Since as described above we expect that visual acuity at age 10 will be skewed, for the multivariate analyses using linear regression, we will explore transformations of visual acuity to a less skewed distribution that also addresses the issue of lower threshold values for patients with extremely poor vision. Another approach we will investigate is categorizing visual acuity into 2 categories depending on whether or not the patient's vision is within normal limits (Driver et al., 2008) and using logistic regression to evaluate the relationship with baseline characteristics.

**Adverse Events and Additional Ocular Surgery:** The occurrence of adverse events and the need for additional ocular surgery will also be assessed (see the age 10 exam CRFs in Appendix 8). For those events and surgery that are specific to the IOL group, we will provide point and confidence interval estimates of the percent of patients experiencing those events. For events that apply to both treatments, we will apply the methods described above for glaucoma.

**Ocular Alignment:** The occurrence, type and extent of deviations will be described with basic descriptive statistics. Life table methods will be used to estimate the probability of being non-orthophoric at each of the follow-up visits and the development of strabismus over time will be compared between the treatment groups using the log-rank test. Patients who undergo strabismus surgery will be classified as non-orthophoric at the time of surgery

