### **Inclusion Enrollment Report**

We enrolled 114 children in IATS between 12/04 and 1/09. All study patients were between the ages of 28 and 210 days at the time of enrollment. The patients all had a unilateral congenital cataract and the fellow eyes were normal. Only infants were enrolled in the study because our goal was to compare two optical treatments for infants following infantile cataract surgery. The ethnicity and gender of the patients enrolled in IATS is shown in Table 7. The clinical trial is being conducted at 12 clinical sites. The DCC and the chairman's office are located at Emory University.

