### Phase 3 Definition and Diagnosis of Glaucoma:

In Phases 1 and 2, an eye was defined as having glaucoma if the following criteria were present: IOP >21 mmHg with one or more of the following anatomical changes: 1) corneal enlargement; 2) asymmetrical progressive myopic shift coupled with enlargement of the corneal diameter and/or axial length; 3) increased optic nerve cupping defined as an increase of  $\geq 0.2$  in the cup-to-disc ratio, or 4) the use of a surgical procedure for IOP control. An eye was defined as glaucoma suspect if any of the following criteria were present: 1) two consecutive IOP measurements >21 mmHg on different dates after topical corticosteroids had been discontinued without any of the anatomical changes listed above; or 2) glaucoma medications were used to control IOP without any of the anatomical changes listed above.

In Phase 3, an eye will be defined as having glaucoma if the following criteria are present: 1) IOP > 21mmHg; and 2) a progressive increase in cup-disc ratio, cup-disc asymmetry of  $\geq 0.2$ , or focal rim thinning. An eye will be defined as glaucoma suspect if any of the following criteria are present: 1) IOP > 21mmHg; or 2) glaucoma medications are being used to control IOP; or 3) an optic disc suspicious for glaucoma (e.g. increased cup-disc ratio). The criteria which will be used to diagnose glaucoma in Phase 3 will be the same as the criteria used in Phases 1 and 2 of the IATS, with the exception of ocular enlargement criteria. Unlike infants, children aged 5-10 years do not usually exhibit signs of ocular enlargement with elevated IOP. The criteria which will be used to diagnose glaucoma suspect in Phase 3 will also be the same as the criteria used in Phases 1 and 2 of the IATS with the exception that two consecutive IOP measurements >21 mmHg at two different visits will not be included in the definition since children in Phase 3 will only be examined once. In addition, since optic disc photographs will be taken at the 10Y exam, we have added a suspicious optic disc as another criterion for Phase 3. Since some children may be diagnosed as having glaucoma or glaucoma suspect between the five and 10 year evaluations, a review of medical records will be performed for all patients to determine who are classified as glaucoma or glaucoma suspect for Phase 3. This will assist in establishing diagnostic criteria and the age of onset for study purposes.

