### **Informed Consent and Assent**

At the 5Y visit, all caregivers were asked to give written permission for the study staff to maintain contact after the closeout visit. If the parents(s) or legal guardian(s) have agreed to have their child return for a study visit at age 10 years, the study will be discussed with them and with the child. Written informed consent must be obtained from the parent(s) or legal guardian(s) of the child before performing any procedures that are not part of the patient's routine care. In addition, because these children are now old enough to assent to their medical treatment, they must give verbal assent or sign an approved Assent Form. If the child has been followed by a non-study ophthalmologist since the 5y visit, the caregiver will be asked to sign a Medical Records Release form in order to capture the interim history.

The accompanying Caregiver will be asked to fill out a brief form regarding the child's use of optical correction, occlusion therapy, or special education services.

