## **Examination Schedule**

Clinical examinations will be performed by IATS certified physicians and visits will be scheduled by the IATS certified clinical coordinator. Study visits will be scheduled for sometime in the year after children have reached 10 years of age and ideally around 6 months after the birthday. Non-study visits may be performed at the discretion of the investigator.

10.0 Years
Examination Information, Interim History, Reading
Manifest Refraction, Cycloplegic E-ETDRS Vision
Clinical Examination: Motility/Stereo, Biomicroscopy, Biometry/keratometry, Tonometry, Pachymetry , Cycloplegic Refraction,
Imaging Optic Disc Photos, Nerve Fiber Layer OCT, Anterior Chamber OCT

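### Does the exploratory time-to-glaucoma curve need a stated event time for cases first found at the 10-year visit?

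*Combined protocol and SAP*

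**What the plan says.** The Statistical Analysis section of Chapter 5 makes Fisher's exact test on the percentage with glaucoma or glaucoma suspect the main comparison. It then says the team will also look into survival methods: "the product-limit method to estimate the probability of developing glaucoma/glaucoma suspect versus time after surgery", a log-rank test and proportional hazards regression. It warns that these may be problematic "depending on how successfully we are able to determine the date of diagnosis", particularly between ages 5 and 10, when children are not seen within the study.

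Two other sections supply dates. Under Phase 3 Definition and Diagnosis of Glaucoma, "a review of medical records will be performed for all patients", partly to establish age of onset. Under Informed Consent and Assent, if a child has been followed by a non-study ophthalmologist, "the caregiver will be asked to sign a Medical Records Release form in order to capture the interim history".

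The Examination Schedule places the visit "sometime in the year after children have reached 10 years of age and ideally around 6 months after the birthday". If visits depart from the target date, the Statistical Analysis section says "we will adjust for the time of the outcome measurement in our analyses as appropriate". No section states an event time, or an interval-censored method, for a case first detected at the visit.

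**The concern.** A product-limit curve needs a time for every event. Records can date a case diagnosed before the visit, but not one that first comes to light there. Such cases are likely: a single raised pressure or a suspicious disc now suffices for suspect status, and disc photographs are new in Phase 3.

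The simple coding dates these cases at the visit and censors unaffected children at their own visits. Every child not already classified then leaves the risk set at the visit, as an event or as a censored observation. Censoring is tied to outcome, and the curve need not agree with the raw percentage in the same children. At stake would be a published curve at odds with the Fisher percentages, over the very years in which the investigators expect the arms to separate.

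**Working it through.** **Figures in the documents.** No product-limit estimate is stated. The nearest figures reproduce: the age-1 comparison, taken as 9/57 against 5/57, gives Fisher p = 0.393 (stated 0.39), and 35% in the contact lens (CL) arm at 5 years is 20/57 = 35.1%.

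**Inputs.**
- 57 children in the CL arm, 20 affected by age 5 (Chapter 5, Study Design and Glaucoma).
- Surgery age: enrollment age, 28–210 days (Inclusion Enrollment Report), taken as uniform (assumed).
- Visit age: 10 to 11 years (Examination Schedule), taken as uniform (assumed).
- Late conversion among the 37 unaffected at 5: 20% (assumed).
- Share q of late cases dated from records: 0, 50 or 80% (assumed).

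The raw 10-year percentage is (20 + 0.2 × 37)/57 = 48.1%.

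**Formula.** Of the children still unclassified at the visit, a fraction h = 0.2(1 − q)/(1 − 0.2q) are cases. If F(t) is the proportion of visits completed by time t after surgery, and record-dated onsets precede t, visit dating gives

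S(t) = (37/57)(1 − 0.2q)(1 − F(t))^h.

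F(10.0) is the mean surgery age, 119/365.25 = 0.326. F(10.25) = 0.326 + 0.25 = 0.576. F(10.5) = 0.820, after a small correction because surgery age can exceed half a year.

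**Results, 1 − S(t), against a raw 48%:**

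| Years after surgery | q = 0 | q = 0.5 | q = 0.8 | At risk |
|---|---|---|---|---|
| 10.0 | 40.0% | 44.1% | 46.5% | 25 / 22 / 21 |
| 10.25 | 45.3% | 46.9% | 47.7% | 16 / 14 / 13 |
| 10.5 | 53.9% | 51.7% | 49.8% | 7 / 6 / 6 |

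Simulation of arms of 57 agrees within about half a point (at 10.0 years 40.2% and 46.2%, at 10.5 years 54.2% and 50.1%, for q = 0 and 0.8).

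**Where the curve crosses the raw value.** This happens when (1 − F)^h = 1 − h. For q = 0, 1 − F = 0.8^5 = 0.328, which leaves 37 × 0.328 = 12 children at risk. For q = 0.8 it is 11. The excess therefore sits in roughly the last dozen children.

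**Noise.** The binomial standard error of the raw figure is √(0.48 × 0.52/57) = 6.6 points. The simulated SD of the curve is about 6.6 points at 10.0 years and 8 to 9 at 10.5.

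**Sensitivity.**
- With other visit and surgery-age shapes, the curve reads about 36–47% at 10.0 years and 49–64% at 10.5.
- At 10.25 years, visits peaked at age 10.5 give 46.1–47.9%; early-weighted visits give 49.6–52.8%.
- Late conversion of 9% (raw 41%) gives 37–40% and 42–44% at 10.0 and 10.5 years. Conversion of 43% (raw 63%) gives 45–59% and 67–69%.

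**Other codings.** Midpoint dating of visit-found cases between age 5 and the visit gives 48.0% at both 10.0 and 10.5 years (q = 0), or 47.8% and 48.7% (q = 0.8). One common nominal 10-year time ends the curve at the raw percentage in every case simulated.

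**Between-arm test.** With no late case dated from records, simulated log-rank type I error is 4.8% with visit dating and 5.1% with a nominal time.

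**The case for a change.** The best argument for a change is that the omission is real, the mechanism is systematic and the remedy costs a sentence or two. Sampling noise does not excuse an avoidable bias: at 10.0 years with no record-dated cases, the shortfall is 8 points, more than one standard error. The low reading at 10.0 years appeared under every visit and surgery-age distribution tried. The high reading at 10.5 years appeared under all but one, where the excess was about 1 point. The same methods are to be reused for glaucoma alone and for adverse events common to both arms. The background on glaucoma also hopes to learn whether age of onset differs between arms, and a rule fixed in advance removes a choice made after seeing the data.

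The mechanism and its direction stand. The need for a protocol change does not. The 8-point gap requires the record review to date nobody; at 80% dated it is under 2 points. The excess at 10.5 years comes from a nearly empty risk set that displayed numbers at risk would expose, and its size moves with an unknown visit distribution.

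A prescriptive remedy has loose ends too. A nominal time later than every recorded diagnosis cannot be fixed in advance, because visits run to age 11. Censoring non-attenders at their last negative examination would have to be squared with the available-case and multiple-imputation approaches already planned. Interval-censored estimation has edge distortion of its own: with none dated, the Turnbull estimate reads 45.7% at 10.0 years and 51.6% at 10.5.

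**Conclusion.** No change is called for. A coding detail is missing from an exploratory analysis that the plan itself makes conditional on usable diagnosis dates. An analyst with the record-review results in hand can choose a sensible coding and show numbers at risk.

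Under the least favourable common coding, the CL-like curve is 2 to 8 points low at 10.0 years after surgery and 2 to 6 points high at 10.5 years. At 10.25 years it is within 3 points of raw for uniform visits or visits peaked at age 10.5, though up to about 5 points high for early-weighted visits. These sizes rest on the assumed 20% late conversion, 0–80% record dating and the stated visit patterns; none comes from the documents. The Fisher comparison is untouched, log-rank size holds in simulation, and no between-arm conclusion depends on the choice.
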